#### 5.2 Exclusion Criteria

- 1. Participants may not be receiving treatment with any investigational drug or investigational biologic within 30 days of randomization or at any time during the study.
- 2. Women with a history of allergic reactions attributed to compounds of similar chemical or biologic composition to Tamoxifen.
- 3. Pregnant women are excluded from this study because the effects of 4-OHT gel on the developing human fetus at the recommended dose and route are unknown.
- 4. Pregnancy (independent of outcome) and/or lactation within 1 year prior to the screening mammogram.
- 5. Women with previous history of cancer (including invasive or intra-ductal breast cancer) except for non-melanoma skin cancer.
- 6. Women who have had a prior mastectomy (unilateral/bilateral), segmental mastectomy, reduction mammoplasty or breast augmentation including implants.
- 7. Women with surgical breast biopsy(s) performed within 3 years or core biopsy(s) performed within 1 year prior to randomization.
- 8. Women with an abnormal mammogram (BI-RADS final assessment category 3 probably benign, 4-suspicious, or 5-malignant findings). Women with BI-RADS 0 assessment (needs additional imaging evaluation) that are subsequently found to have negative (BI-RADS 1) or benign findings (BI-RADS 2), are NOT excluded.
- 9. Women with only synthetic 2D mammograms generated from 3D (tomosynthesis) are excluded as breast density measurements are not yet validated for synthetic mammograms. Women with combination 2D+3D mammograms are not excluded.
- 10. Women with active liver disease or thromboembolic disorder.

- 11. Women with skin conditions such as psoriasis, fungal infections, keloids etc., or tattoos and/or piercings that in the opinion of the Investigator, would interfere with absorption of the investigational product.
- 12. Women who have had an abnormal gynecology exam within the last three years with clinically significant findings, such as secondary dysmenorrhea, polyps, or atypia, which in the opinion of the Investigator would interfere with the study.
- 13. Women who have received treatment with Selective Estrogen Receptor Modulators (SERMs) (e.g. tamoxifen, raloxifen) or aromatase inhibitors.
- 14. Women taking estrogen containing contraceptives or Hormone Replacement Therapy (HRT) must discontinue the treatment a minimum of 6 months prior to the screening mammogram. Progestin only contraceptives are permitted.
- 15. Women with a concurrent illness, disease or condition that, in the opinion of the Investigator, would limit their compliance with study requirements or place them at additional risk.

#### 5.3 Dose Reduction

If a subject experiences toxicity that may make her want to stop taking study drug, the dose of study drug will be reduced by 50%, to 2 mg (1 pump actuation) to each breast. The reduced dose will be maintained for the duration of the study.

## 5.4 Early Withdrawal of Subjects

A subject is free to withdraw from the study at any time for any reason without prejudice to their future medical care by the physician or at the institution. The Investigator or Sponsor may also withdraw the subject at any time in the interest of subject safety. The primary reason for withdrawal must be recorded in the subject's medical record and on the withdrawal form in the Case Report Form (CRF). If a subject is withdrawn for more than one reason, each reason should be documented in the source document and the most medically significant reason should be entered on the CRF. The withdrawal of a subject from the study should be discussed where possible with the Medical Monitor before the subject stops administration of the study drug. If the study drug is discontinued, the final evaluations will be performed as completely as possible. Any comments (spontaneous or elicited) or complaints made by the subject and the reason for termination, date of stopping study drug, and the total amount of study drug administered must be recorded in the CRF and source documents.

## 5.5 Subject Replacement

Randomized subjects who do not complete the study for any reason will not be replaced.

## 6.0 TREATMENT OF SUBJECTS

Investigational product will only be shipped to Investigators who have provided BHR PHARMA, LLC (or an authorized representative) all required study documents, including Institutional Review Board (IRB) approval, have executed a clinical trial agreement (CTA), and have been approved by BHR PHARMA, LLC to begin the study. Study drug will be provided by BHR PHARMA, LLC (or authorized representative) as blind-labeled ready-to-use canisters containing 4-OHT gel or placebo.

# 6.1 Blinding and Unblinding

[figure not shown]
All Investigator site personnel will be blinded to treatment assignment. The Investigator (or designee) will be responsible for drug accountability and dispensing of the study drug.

In the case of an AE or serious adverse event (SAE) for which the Investigator must know a specific treatment allocation to ensure the subject's safety, unblinding of treatment assignment is permitted. Instructions for "breaking the blind" will be provided to the Investigator. It should be stressed that unblinding the treatment allocation is only allowed for safety concerns in an emergency. If time allows, the Investigator is encouraged to discuss the matter with the study Medical Monitor prior to "breaking the blind" whenever possible.

If possible, the relationship of the AE to the study drug should be assessed before the treatment code is broken. In all cases, the Medical Monitor must be notified within 24 hours after the code has been broken.

If the treatment assignment is unblinded, study drug will be discontinued and the subject's participation in the study will end.

# 6.2 Formulation, Packaging, and Labeling

canisters will be labeled with a canister identifier and 'For Investigational Use Only'.

#### 6.3 Investigational Product Storage

All study drug must be stored in a secure limited-access area, at controlled room temperature  $(20 - 25^{\circ} \text{ C} [68^{\circ} \text{ to } 77^{\circ}\text{F}]$ ; excursions are permitted to  $15^{\circ}$  to  $30^{\circ}\text{C} [59^{\circ} \text{ to } 86^{\circ}\text{F}]$ ) in accordance with labeled storage requirements. Subjects will be instructed to store the study drug at home at room temperature, and to avoid extreme heat or cold during transportation from the clinic to home. Investigational labeling will include instructions to keep the product out of the reach of children.

#### 6.4 Dispensing

The Investigator (or designee) will only dispense the specific numbered canisters/study drug kit as allocated by an interactive, web-based tele-randomization system.

#### 6.5 Dosage and Administration

The first dose of treatment will be applied under the supervision of the PI or designee at the clinical site. Thereafter, subjects will self-apply either BHR-700 gel or placebo as 2 fixed unit doses daily to each breast. The gel should not be applied to any other parts of the body, including the neck, abdomen, or genitals. It is advised to apply study drug in the morning after showering and to wash hands with soap and water after application. Night-time application is acceptable, but caution should be taken to limit transfer to other individuals. Application should occur approximately at the same time daily. A subject study drug administration guideline is provided in Appendix 2.

When a canister is used for the first time, it must be primed. To prime the canister, remove the cap from the canister and push the pump all the way down until gel is dispensed. Complete the priming process by pushing the pump all the way down an additional three (3) times. Do not use any gel that comes out while priming. Discard the gel by washing it down the sink to avoid accidental exposure to others. It is only necessary to prime the pump before the first dose is dispensed. Repeat priming each time a new canister is opened. After priming, the canister is ready to use. One complete press of the pump will deliver approximately the same amount of gel each time. The Investigator (or designee) will demonstrate this to each subject and will prime the study drug canister(s) prior to dispensing to the subject.

If a subject misses a dose by more than 12 hours, that dose should be noted as missed and the subject should wait for the next scheduled time before applying investigational product.

If a subject experiences toxicity that may make her want to stop taking study drug, the dose of study drug will be reduced by 50%, to 2 mg (1 pump actuation) to each breast. The reduced dose will be maintained for the duration of the study.

## 6.6 Investigational Product Administration Precautions

Following the initial application by the Investigator (or his/her designee) only the subject should apply the study drug. Others (such as the subject's family members) should not apply the study drug to the subject.

The subject should not make contact with the area of skin where the study drug was applied for at least 1 hour after the application. Subjects should not massage or rub in the gel and allow the gel to dry for 5 minutes before getting dressed.

If someone else is exposed to the study drug by direct contact with the study drug, that person should wash the area of contact with soap and water as soon as possible. The longer the study drug is in contact with the skin the greater the chance that the other person will absorb some of the study drug. **This is especially important for children.** 

No skin-to-skin transfer studies with BHR-700 (4-OHT gel) have been conducted. However, a study conducted in women¹⁶ with a FDA-approved product, EstroGel® (0.06% estradiol gel), using a similar formulation showed that skin-to-skin contact between treated and non-treated women 1 hour after application of the gel, neither resulted in a statistically significant or clinically important transfer of estradiol gel to the non-treated women nor was there subsequent absorption of estradiol by the non-treated women. Use of health and beauty products (lotions, creams, sunscreen, self-tanner, etc.) on the application site is allowed one (1) hour after application of the study gel.

## 6.7 Pregnancy and Nursing

The effects of 4-OHT gel on the developing human fetus at the recommended dose and route are unknown. For this reason, women of childbearing potential must agree to avoid pregnancy by using a reliable medically acceptable contraceptive method.

A woman is not considered to be of child bearing potential if she has:

- a. Serum follicle-stimulating hormone (FSH) levels consistent with menopause and has had complete amenorrhea for at least 12 months prior to starting drug.
- b. Documented surgical history of hysterectomy or bilateral oophorectomy/salpingo-oophorectomy.

A woman of child bearing potential must use one of the following contraceptive methods throughout the study and for at least 90 days after completing the study:

- a. Bilateral tube ligation performed 6 months or more prior to starting study drug.
- b. Consistent monogamous relationship with a male partner who has had a medically proven vasectomy performed 6 months or more prior to starting study drug.
- c. Intrauterine device (IUD) in place for at least 3 months before starting study drug.
- d. Progestin-containing hormonal birth control (oral, transdermal, injectable, or implantable) used consistently and successfully for at least 3 months prior to starting study drug.
- e. Double barrier contraception with spermicide, including a condom plus diaphragm or cervical cap. **Note:** Female condom should be used with male condom (as a double barrier method of contraception) due to risk of tearing.
- f. Abstinence

True abstinence, when this is in line with the preferred and usual lifestyle of the subject, is acceptable. Periodic abstinence (e.g., calendar, ovulation, symptothermal, post-ovulation methods) and withdrawal are not acceptable methods of contraception.

There is an unknown but potential risk for AEs in nursing infants secondary to treatment of the mother with 4-OHT gel. Therefore, it is required that breastfeeding be discontinued prior to the mother enrolling in this study (see also 5.2, exclusion criterion 4).

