#### 6.11 Prohibited Concomitant Medications/Therapies

Investigational drugs or therapies should not be used at any time during the study because of their potential to confound the results. The following drugs or therapies are prohibited during the study because of their potential to confound the results:

- Application of prescription or OTC topical drug products (including but not limited to: gel, patch, cream, ointment, lotion, or spray) to the study drug application site(s), i.e., on the breast(s).
- Prescription or OTC treatments that are known/suggested to have an estrogenic or antiandrogenic effect including SERMs and aromatase inhibitors.

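### Protocol section 6.7(d) accepts hormonal contraceptives that contain a progestin without ruling out estrogen, while exclusion 14 allows only progestin-only products and section 6.11 bars estrogenic treatments

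*Protocol*

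**What the plan says.** Four places in the Protocol bear on hormonal contraception.

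- **Section 6.7 (Pregnancy and Nursing).** The lead-in, whose last interval is counted from study completion, reads "A woman of child bearing potential must use one of the following contraceptive methods throughout the study and for at least 90 days after". Item (d) of the list is "Progestin-containing hormonal birth control (oral, transdermal, injectable, or implantable) used consistently and successfully for at least 3 months", counted back from the first dose. Nothing in the item, or elsewhere in 6.7, limits it to products without estrogen.
- **Section 5.2, exclusion 14, repeated in the synopsis (section 1.3).** "Women taking estrogen containing contraceptives or Hormone Replacement Therapy (HRT) must discontinue the treatment a minimum of 6 months prior to the screening mammogram". The criterion then adds: "Progestin only contraceptives are permitted".
- **Section 6.11 (Prohibited Concomitant Medications/Therapies).** The lead-in is "The following drugs or therapies are prohibited during the study because of their potential to confound the results", and one of the listed classes is "Prescription or OTC treatments that are known/suggested to have an estrogenic or antiandrogenic effect including SERMs and aromatase inhibitors". Contraceptives are not named, and no exception is made for methods accepted in 6.7.

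Section 6.7 does point the reader to exclusion 4 for breastfeeding. It does not point to exclusion 14 or to 6.11 for hormonal methods.

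On handling afterwards, Protocol section 9.6 leaves the description of major deviations to the SAP and their identification to the sponsor before lock. SAP section 2.1 repeats that the sponsor side identifies them before lock and unblinding. SAP section 3.5 plans listings. Neither document says how estrogen-containing contraceptive use is to be classified.

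**The concern.** Progestin-containing and progestin-only describe different sets of products. A combined estrogen-progestin product belongs to the first and not to the second. The same product therefore falls within the wording of the accepted list in 6.7 and outside what exclusion 14 and 6.11 allow.

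This matters because the study drug is an anti-estrogen. Protocol section 2.1 describes estradiol as stimulating normal breast epithelium and tamoxifen as competing with it at the receptor. Change in breast density is the primary endpoint, and the Protocol itself treats estrogenic treatment as a possible confounder of the results. A site that checks contraception against 6.7 alone could accept a product that two other sections forbid. Such a woman would have an exposure the Protocol meant to keep out, and no text states how her case is to be coded.

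**Working it through.** There is no stated figure to reproduce and no sample-size or error-rate quantity is involved. The check is a comparison of the rules, with one piece of arithmetic on the time windows.

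**1. Product wording**

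| Product | 6.7(d) | Exclusion 14 | 6.11 |
|---|---|---|---|
| Progestin-only | accepted | permitted | not named |
| Combined estrogen-progestin, in current use | within the wording | must have been stopped | caught by the estrogenic-effect class |

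The conflict is in the second row. Section 6.11 reaches combined contraceptives only through its general description of effect.

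**2. Time windows**

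Inputs:
- Exclusion 14: off estrogen for at least 6 months before the screening mammogram.
- Sections 7.1 and 8.8: the mammogram falls within 3 months before randomization, so 0 to 3 months before.
- Section 7.2: randomization and first dose are both on Day 1.
- Section 6.7(d): at least 3 months of use before study drug.

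Minimum time off estrogen at first dose = 6 + (0 to 3) = 6 to 9 months.

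A woman who meets 6.7(d) with a combined product has been taking it during the 3 months up to first dose. She cannot also have been off it for the preceding 6 to 9 months. Anyone who satisfies 6.7(d) by means of a combined product therefore fails exclusion 14.

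A progestin-only user can satisfy both: 3 months on her method and at least 6 to 9 months without estrogen. One window is time established on a method and the other is time off estrogen, so they are compatible. The contradiction lies in the description of the product.

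**3. Which rule a site would meet, and when**

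Exclusion 14 is applied at screening and reaffirmed before dosing (sections 7.1 and 7.2, Appendix 1), and section 10.7 lets investigators enrol only women who meet the criteria. Section 6.11 applies during the study. Section 6.7 waives neither. Read together, the sections give one answer: a current user of a combined product is not eligible. Read alone, 6.7 gives another, and it does not send the reader to the sections that would correct it.

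**4. What depends on it now**

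- SAP section 3.3.2 plans no efficacy analysis for the study report. Density may be analysed ad hoc (SAP sections 3.3.2 and 3.8).
- The per-protocol population appears in no planned table in SAP sections 4 and 5. It appears only in the listing of deviations leading to exclusion from it (LPD02a).
- Hormone and coagulation summaries are still planned (SAP sections 3.6 and 4.1.3).
- Density and BI-RADS values are still listed (SAP section 4.2.3).

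**The case against.** The strongest reply is that the requirements are cumulative. Section 6.7 sets a contraception duty and does not replace eligibility or the prohibited-medication rule. Exclusion 14 appears twice, is checked at screening and again before dosing, and 6.11 covers the treatment period. Meeting one requirement while failing another does not make a woman compliant. This stands, and it limits the point to a wording conflict that could mislead a site. It does not show that the Protocol admits combined-product users.

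A reader might infer more in several directions. The documents do not support these inferences.

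- *That 6.7(d) lets a woman start a combined product during the trial.* The item requires use for at least 3 months before study drug. A product first taken after that does not meet it, and 6.11 forbids it.
- *That per-protocol status would differ from site to site.* Sites do not assign it. The sponsor identifies major deviations centrally before lock.
- *That 3 months and 6 months contradict each other.* They measure different things, as shown above.
- *That density change would be pulled toward no effect.* The documents give no effect of contraceptive estrogen on change in density. Steady use at both mammograms, starting between them and stopping between them need not act alike.
- *That a count of affected women can be given.* No usage figure is reported. Only women of childbearing potential fall under 6.7, and SAP section 1.3 says fewer subjects were available than planned.

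**Conclusion.** The inconsistency is real. Section 6.7(d) accepts progestin-containing methods with no estrogen condition, exclusion 14 permits progestin-only methods, and 6.11 prohibits estrogenic treatments. By their literal wording they disagree about combined products, and 6.7 lacks the cross-reference that would resolve the disagreement for a site using it alone.

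Its size is modest. The effect on the primary endpoint cannot be quantified or signed from the documents, nor can the number of women. With no efficacy analysis planned for the report, what remains exposed is the deviation listings, the hormone and coagulation summaries, and any ad-hoc density analysis.

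The conclusion rests on two readings: that a combined product counts as progestin-containing because it contains a progestin, and that 6.11's estrogenic-effect class includes estrogen-containing contraceptives although it does not name them. A reader might also take 6.11 to be about density specifically. Its stated reason is confounding of the results in general, and exclusion 14 gives no reason, although its window is tied to the screening mammogram.

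**What to change.** 1. Reconcile section 6.7(d), exclusion 14 in sections 1.3 and 5.2, and section 6.11 so that they make one consistent statement on estrogen-containing contraceptives. Which contraceptive rule is right is a clinical decision for the sponsor and is not judged here.
2. Add a cross-reference in 6.7 to exclusion 14 and to 6.11, as 6.7 already does for exclusion 4.
3. At the sponsor's central deviation review before lock, define how estrogen-containing contraceptive use is classified and apply that one definition to every subject, for both the general deviation listing and the listing of exclusions from the per-protocol population.

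The cost is a few words in the Protocol and one line in the deviation definitions. No new data are needed for use during the study: Protocol section 6.10 already records the name, dose, route, dates and indication of every medication taken. Since the trial was stopped early, the third step is the one that still bears directly on the report; the first two matter if the Protocol text is amended or reused.

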## **Procedure for Reporting Pregnancy Exposure and Birth Events**

Should a female subject become pregnant or be suspected of being pregnant while participating in this study, the event must be reported to the Medical Monitor upon receipt of information by the study staff. While the pregnancy itself is not considered to be an AE or SAE, any pregnancy complications should be recorded as AEs or SAEs (if applicable). Any pregnancy will be followed through delivery for the observation of any SAEs. Fatalities and spontaneous abortions must be reported as SAEs.

#### 6.8 Assessment of Compliance

Study drug compliance will be checked at each study visit. Subjects will be asked to capture daily gel administration in a diary and drug canisters will be weighed on release to the subject and on return. The canister weight will be recorded in grams. If the study drug is discontinued or interrupted, the reason(s) will be recorded. One or more extra canisters will be provided to cover loss. Subjects who are found to be non-compliant will be re-trained on study drug administration by the PI or designee.

#### 6.9 Investigational Product Accountability

The Investigator will maintain accurate records of the disposition of all clinical drug supplies received during the study and the dates on which drug supplies were received from BHR PHARMA, LLC or authorized representative. At the conclusion of the study, any unused study gel will be destroyed by the site in accordance with their standard operating procedures (SOP), upon written authorization by BHR PHARMA, LLC and pursuant to applicable federal and state regulations or returned to BHR PHARMA, LLC or their designee.

